#### **6 INVESTIGATIONAL PRODUCTS**

# 6.1 Formulation, Packaging, and Administration

#### 6.1.1 NasoVAX

NasoVAX uses the RespirVec platform developed by Altimmune for intranasally administered vaccines, an E1/E3-deleted, RD-Ad5 vector that expresses the protein of interest within respiratory epithelial cells. In the case of NasoVAX, the vector contains a genetic insert encoding the HA surface protein antigen from influenza type A or B. The recombinant Ad5 vector lacks the E1 region of the viral genome (nucleotides 343 to 3511), which renders the virus RD and incapable of producing infectious virus particles upon entry into a host cell. An additional deletion of nucleotides 28132 to 30813 in the E3 region of the vector removes genes that are involved in evading the host immune response and are dispensable for virus replication. An expression cassette consisting of a cytomegalovirus transcriptional enhancer/promoter to drive the expression of the HA gene, a bioengineered HA gene, and a Simian Virus 40 polyadenylation signal has been inserted in place of the E1 gene sequences. Figure 1 provides a schematic diagram of the RD-Ad5 vector and identifies those sequences from the parent adenovirus genome that are retained in the vector.

Figure 1 Schematic Diagram of the Adenovirus Vector

Numbers refer to base pair# in wild-type Ad5 sequence, GenBank ID AY339865.1.

In this trial, the vector will contain a genetic insert encoding the HA surface protein antigen from an A/California/04/2009(H1N1)-like strain of influenza (AdcoCA09.HA).

NasoVAX is manufactured by propagation of the RD-Ad5 vector in replication-permissive PER.C6 cells, followed by purification of the virus from the infected cell harvest, and the final product includes the following excipients: Tris HCl (pH 7.4), histidine, sucrose, sodium chloride, magnesium chloride, polysorbate 80, ethylenediaminetetraacetic acid, and ethanol.

05 October 2017 Confidential Page 28 of 66

NasoVAX will be supplied in single-use glass vials each containing a nominal volume of 0.7 mL of a sterile, frozen suspension of vaccine formulated to deliver the nominal doses of  $1 \times 10^9$ ,  $1 \times 10^{10}$ , or  $1 \times 10^{11}$  vp. According to the release specifications for NasoVAX, the actual dose to be administered may be up to approximately 3-fold lower or higher than the nominal dose. The 0.5 mL NasoVAX doses will be administered as an intranasal spray using a 1 mL syringe fitted with a Teleflex LMA MAD Nasal Intranasal Mucosal Atomization Device. Further information on dose preparation and administration is provided in the pharmacy manual.

#### 6.1.2 Placebo

The placebo is normal saline provided by the investigational site.

The 0.5 mL placebo doses will be administered as an intranasal spray using a 1 mL syringe fitted with a Teleflex LMA MAD Nasal Intranasal Mucosal Atomization Device and will be identical in appearance to NasoVAX doses. Further information on dose preparation and administration is provided in the pharmacy manual.

# 6.2 Labelling

All IPs will be labelled in accordance with applicable regulatory guidelines.

# 6.3 Storage

NasoVAX will be stored in a secure place under appropriate storage conditions at  $-20^{\circ}\text{C} \pm 5^{\circ}\text{C}$ . Normal saline will be stored in a secure place in accordance with storage conditions on the product label.

# 6.4 Blinding and Unblinding

Investigators, subjects, and all study staff with direct subject contact will be blinded to assignment to NasoVAX or placebo. A designated unblinded pharmacist (or otherwise qualified person) at the site will assign the NasoVAX or placebo based on the block randomization table provided by the unblinded statistician and prepare the blinded syringe for dispensing to the subject. The individual performing these tasks will have no contact with the subjects and minimize contact with other site study personnel.

Unblinding of vaccine assignment is discouraged. In the event of a medical emergency, for which the identity of the assignment is critical to the care of a subject, the Investigator will call the Medical Monitor to discuss. In the event that unblinding is deemed necessary, a designated unblinded study team member will provide the assignment to the Medical Monitor who will provide the information to the Investigator.

Sponsor personnel and other members of the study team will have no access to data aggregated by treatment arm until after the interim analysis (see Section 12.10). Sponsor personnel and other members of the study team will have no access to any individual treatment assignment except as needed to satisfy requirements for prompt reporting of SAEs to Regulatory Authorities. In this case, unblinded data from an individual subject will be provided immediately to the Medical Monitor

05 October 2017 Confidential Page 29 of 66

# 6.5 Randomization and Timing of NasoVAX/Placebo

Subjects will be enrolled into 3 sequential cohorts of 20 subjects each defined by the viral particle dose  $(1\times10^9, 1\times10^{10}, \text{ or } 1\times10^{11} \text{ vp})$ . Within each sentinel group and cohort, subjects will be randomized at a ratio of 3:1 ratio to receive 1 intranasal dose of NasoVAX or placebo on Day 1.

A sentinel cohort of 5 subjects from each cohort will be dosed. Dosing of the remainder of each cohort may proceed after the last sentinel subject completes Day 8 if no events meeting stopping criteria (Section 6.6) have occurred. The SRC, consisting of the Investigator, the Medical Monitor, and a Sponsor Representative, will review all AE, reactogenicity, and laboratory data through Day 8 for all subjects in each cohort before subjects are randomized to the next higher dose.

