This is a Phase 2a, randomized, double-blind, placebo-controlled trial to evaluate the safety and immunogenicity of NasoVAX in healthy adults 18 to 49 years of age. Subjects will be screened within 28 days of randomization (Day 1). Approximately 60 subjects who meet all inclusion and no exclusion criteria and provide written informed consent will be enrolled into 3 sequential cohorts of 20 subjects each defined by the viral particle dose  $(1 \times 10^9, 1 \times 10^{10}, \text{ and } 1 \times 10^{11} \text{ vp})$ . Within each cohort and its sentinel group, subjects will be randomized in a 3:1 ratio to receive 1 intranasal dose of NasoVAX or placebo (Day 1).

A sentinel cohort of 5 subjects from each cohort will be dosed. Dosing of the remainder of each cohort may proceed after the last sentinel subject completes Day 8 if no events meeting stopping criteria have occurred. The Safety Review Committee (SRC), consisting of the Investigator, the Medical Monitor, and a Sponsor Representative, will review all AE, reactogenicity, and laboratory data through at least Day 8 for all subjects in each cohort before subjects are randomized to the next higher dose. If any event meeting the following criteria occurs, the SRC will review all available safety information before additional patients are dosed:

- Occurrence of any related SAE or Grade 4 AE
- Occurrence of 2 Grade 3 AEs in the same organ system
- Occurrence of the same Grade 3 laboratory abnormality in 2 or more subjects

Each subject will record reactogenicity (local events, systemic events, and oral temperature) and whether any medication or treatment was used for the symptom(s) in a diary daily for 14 days after the NasoVAX/placebo dose. Each subject will be contacted by telephone on Day 2 for safety assessment and review of the diary. Subjects will return to the investigational site on Days 4, 8, 15, 29, 91, and 181 for safety and immunogenicity assessments. At each visit, the subject will also be asked about the interim medical history and use of any medications.

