All AEs and medications will be recorded from signing of the ICF to Day 29. Thereafter to the end of the study, only MAEs, NCIs, SAEs, immunosuppressive medications (see list in Appendix 3), and vaccines will be recorded. Samples for clinical laboratory tests (hematology, serum chemistry, urinalysis) will be collected at Screening and on Days 8 and 29. A complete physical examination and vital signs will be performed at Screening and predose on Day 1, and targeted and symptom-driven physical examinations will be performed and vital signs measured 2 hours postdose and on Days 4, 8, 15, and 29. An ECG will be performed at Screening and on Day 29. If a subject experiences acute symptoms compatible with adenoviral infection within 28 days after the NasoVAX/placebo dose, a sample will be collected for viral culture as clinically indicated.

One interim analysis of humoral immunogenicity data and safety data (including summaries of AE, reactogenicity, concomitant medications and vaccines, vital signs, ECG, and laboratory data and listing of any viral culture results) will be conducted when all data through the Day 29 visit is available and monitored for all subjects.

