# 6.6 Stopping Criteria

If any event meeting the following criteria occurs, the SRC will review all available safety information before additional patients are dosed:

- Occurrence of any related SAE or Grade 4 AE
- Occurrence of 2 Grade 3 AEs in the same organ system
- Occurrence of the same Grade 3 laboratory abnormality in 2 or more subjects

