# 7.10 Blood Samples

# 7.10.1 Safety Laboratory Tests

Samples for the following tests will be collected, processed, and shipped to the laboratory in accordance with instructions in the laboratory manual at the time points specified in the Schedule of Events:

- Hematology: hemoglobin, platelet count, white blood cell count with differential (absolute or percent counts of neutrophils, lymphocytes, monocytes, basophils, eosinophils)
- Serum chemistry: alkaline phosphatase, ALT, AST, bicarbonate, bilirubin, chloride, creatine kinase, creatinine, glucose, potassium, sodium, urea nitrogen
- Urinalysis: glucose, protein

05 October 2017 Confidential Page 33 of 66

Any laboratory abnormality deemed clinically significant by the Investigator should be recorded as an AE (see Section 9.5).

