#### 8.2.4 Day 8 (± 1 Day)

The following procedures will be performed:

- Review of diary
- Targeted and symptom-driven physical examination
- Vitals signs
- Concomitant medications (including vaccines) recording
- AE assessment
- Sample collection:
  - o Clinical laboratory tests (hematology, serum chemistry, urinalysis)
  - Serum for humoral response
  - Whole blood sample for isolation of PBMCs for cellular response
  - Nasopharyngeal swab

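### The sentinel hold ends at the Day 8 visit and not on receipt of the Day 8 laboratory results, and the laboratory stopping rule leaves out Grade 4

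*Protocol*

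**What the plan says.** **Release of the rest of a cohort.** Section 6.5 of the protocol reads "Dosing of the remainder of each cohort may proceed after the last sentinel subject completes Day 8 if no events meeting stopping criteria" set out in Section 6.6 have occurred. Sections 1.1 and 4.1 carry the same condition: the remaining subjects "may proceed after the last sentinel subject completes Day 8 if no events meeting stopping criteria have occurred". None of the three mentions laboratory results or a Safety Review Committee (SRC) review at this step.

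**Escalation to the next dose.** Here laboratory data are named. Section 6.5 has the SRC review adverse events, reactogenicity and "laboratory data through Day 8 for all subjects in each cohort before subjects are randomized to the next higher dose".

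**Timing of the samples.** Under Section 4.1 the safety laboratory samples "will be collected at Screening and on Days 8 and 29". Section 8.2.4 places the draw among the Day 8 visit procedures. Section 7.10.1 says the samples "will be collected, processed, and shipped to the laboratory in accordance with instructions in the laboratory manual". No turnaround time is given.

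**Stopping criteria.** Section 6.6 (repeated in 1.1 and 4.1) has three. The only laboratory one is "Occurrence of the same Grade 3 laboratory abnormality in 2 or more subjects". Grade 4 appears only in the adverse event criterion. When a criterion is met, "the SRC will review all available safety information before additional patients are dosed".

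**The concern.** The sentinel step exists to protect the other 15 subjects of the same cohort. Its release condition depends on a laboratory stopping rule, yet the only post-dose laboratory evidence available by then is drawn at the visit whose completion ends the hold. A site could follow the text and begin dosing with some or all of the sentinel results still pending.

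The laboratory rule has a second weakness: it lets the worse finding through. Two subjects in the Grade 3 band meet it. Two subjects in Grade 4, or one in each grade, do not, unless the Grade 4 value has also been recorded as an adverse event.

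The sentinel step matters most in the upper cohorts. Section 2.6 gives 3.3×10^9 vp as the highest earlier intranasal dose, and cohorts 2 and 3 go well beyond it. Section 6.1.1 adds that the actual dose may be up to about 3-fold above or below nominal.

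**Working it through.** The protocol gives no figure for this point. The check is a reading of the timeline and the grading table, with an illustration of size.

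**1. Timeline for one cohort.** Five sentinels are dosed and the remainder is 20 − 5 = 15. No safety laboratory sample is scheduled between dosing and Day 8 (Section 1.2). The Day 8 sample is drawn and shipped at the visit that ends the hold. No spacing between sentinels is prescribed, so if all five are dosed on one day, all five results can be outstanding together.

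**2. Chance that the laboratory rule is met but not yet visible.** Assumptions, not from the protocol: sentinels are independent, each has probability p of one given Grade 3 abnormality, and which results are late is unrelated to their values. For n results,

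P(X ≥ 2 | n) = 1 − (1−p)^n − n·p·(1−p)^(n−1).

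- p = 0.05, n = 5: 1 − 0.77378 − 0.20363 = 0.0226
- p = 0.10, n = 5: 1 − 0.59049 − 0.32805 = 0.0815
- p = 0.02, n = 5: 0.0038

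With k results outstanding, the chance of a missed trigger is P(X ≥ 2 | 5) − P(X ≥ 2 | 5−k). Given exactly 2 of 5 affected, the miss probability is 1 − C(5−k, 2)/C(5, 2).

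| k outstanding | p = 5% | p = 10% | given exactly 2 of 5 |
|---|---|---|---|
| 1 | 2.26 − 1.40 = 0.86% | 8.15 − 5.23 = 2.92% | 1 − 6/10 = 40% |
| 2 | 2.26 − 0.73 = 1.53% | 8.15 − 2.80 = 5.35% | 1 − 3/10 = 70% |
| 3 | 2.26 − 0.25 = 2.01% | 8.15 − 1.00 = 7.15% | 1 − 1/10 = 90% |
| 4 or 5 | 2.26% | 8.15% | 100% |

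The rule counts subjects regardless of arm, hence n = 5. If only vaccinated sentinels were at risk (3 or 4 of the 5 under a 3:1 ratio), P(X ≥ 2) would be 0.7% to 1.4% at p = 5% and 2.8% to 5.2% at p = 10%.

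**3. Subjects exposed meanwhile.** Exposure = min(15, subjects dosed per day × turnaround in days). Both inputs are assumed: 1 × 1 = 1; 3 × 2 = 6; 5 × 3 = 15.

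**4. Grade bands in Appendix 1, for tests on the Section 7.10.1 panel.**

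| Test | Grade 3 | Grade 4 |
|---|---|---|
| Potassium, high (mEq/L) | 5.5–5.6 | > 5.6 |
| ALT, AST (× ULN) | 5.1–10 | > 10 |
| Neutrophils (cells/mm³) | 500–999 | < 500 |

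For these tests Grade 3 is closed at the severe end, so a Grade 4 value is not a Grade 3 abnormality. Two potassium values of 5.5 meet the rule; two of 5.7, or one of each, do not. For urea nitrogen (> 31) and fasting glucose (> 125) Grade 3 is open-ended, so no numeric value is skipped.

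**5. The alternative route for Grade 4.** Section 9.1.1 allows an abnormal laboratory finding to be an adverse event. Sections 7.10.1 and 9.5 have it recorded as one when the investigator judges it clinically significant, and 9.5 makes confirmation by repeat test part of that definition. Section 9.8 asks for confirmation within 48 hours or as clinically indicated. The Grade 3 laboratory rule requires neither step.

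**6. Dose context.** 1×10^10 / 3.3×10^9 = 3.0 for cohort 2; 1×10^11 / 3.3×10^9 = 30.3 for cohort 3.

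**The case against.** The strongest reply is that the release condition has two parts. The last sentinel must finish Day 8, and no stopping event may have occurred. Since one stopping criterion is a laboratory one, a site cannot know that the second part holds until the results are in. That is a reasonable reading, and many sites would wait. It is not the only one: the condition is also satisfied on its face when nothing is yet known, and the next sentence of Section 6.5 shows that laboratory review was spelled out where it was intended.

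On Grade 4, one recorded Grade 4 adverse event in a single subject triggers review, which is stricter than the two-subject Grade 3 rule. The bar in Section 9.5 is also not high, because simply following the value counts as a change in management. Most confirmed Grade 4 values would therefore reach the SRC. What remains is the interval before confirmation, and values that are not confirmed or not judged significant.

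Three further points stand. A late result that meets a criterion still halts dosing under Section 6.6, and escalation is separately protected. The rates, dosing pace and turnaround used above are assumed; turnaround may be given in the laboratory manual, which is not at hand. None of the calculations measures the Grade 4 gap. The top dose is also not unsupported: it equals the no-observed-adverse-effect level in the rabbit repeat-dose study of a similar vaccine (Sections 2.4 and 4.2.2).

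**Conclusion.** Both parts of the concern hold on the protocol's wording. The sentinel hold can end before the laboratory stopping rule has been checked on the sentinels, and that rule, read literally, passes over Grade 4 values for several tests on the panel.

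The size is small. At assumed rates of 5% to 10%, a trigger is present but unseen in about 1% to 8% of sentinel groups, depending on how many results are outstanding; at 2% it is below 0.4%. The number of subjects dosed in the meantime runs from 1 to all 15 under the assumed pace and turnaround, with the full 15 only at the fastest pace considered. No estimate or planned analysis is affected. This is a safety rule for healthy volunteers at doses beyond earlier intranasal experience, and it should not depend on which reading a site adopts. It should be corrected. Confidence is medium, because the size rests on assumed inputs and the intended reading may be the safer one.

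**What to change.** **Release condition (Sections 1.1, 4.1 and 6.5).** State that the remaining subjects of a cohort are dosed only once the Day 8 safety laboratory results of all 5 sentinels have been received and checked against Section 6.6, and no stopping criterion has been met.

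**Laboratory criterion (Sections 1.1, 4.1 and 6.6).** Add the words 'or higher' after Grade 3, so that two Grade 4 values, or one Grade 3 and one Grade 4 of the same abnormality, count.

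This closes the cases described. It does not make a single Grade 4 value that is not recorded as an adverse event trigger review. If the sponsor wants that as well, any Grade 4 laboratory abnormality can be added as a criterion of its own.

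**Cost.** One sentence in three places and two words in three places. In operation, each of the 3 cohorts waits for the laboratory, assumed to be a few days because turnaround is not stated, and the SRC may occasionally review a Grade 4 value that a repeat test does not confirm.

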# 6.6 Stopping Criteria

If any event meeting the following criteria occurs, the SRC will review all available safety information before additional patients are dosed:

- Occurrence of any related SAE or Grade 4 AE
- Occurrence of 2 Grade 3 AEs in the same organ system
- Occurrence of the same Grade 3 laboratory abnormality in 2 or more subjects

# 6.7 Accountability, Dispensing, and Destruction

The Investigator (or designee) will maintain an accurate record of the receipt of each IP as shipped by the Sponsor (or designee), including the date received. In addition, an accurate IP disposition record will be kept, specifying the amount dispensed for each subject and the dates of dispensation and any returns.

Sponsor approval is required for on-site destruction of all used IP and shipment of all unused IP back to the Sponsor at the completion of the study and once all reconciliation has occurred.

#### 6.8 Prior and Concomitant Treatments

All concomitant treatments, including over-the-counter medicines, will be recorded from 30 days before the NasoVAX/placebo dose through 28 days after the NasoVAX/placebo dose and coded using the WHO Drug Dictionary. Only immunosuppressive medication (see list in Appendix 3) and vaccines will be recorded from Day 29 to the end of the study.

#### 6.8.1 Prohibited Prior Medications and Vaccines

Subjects who received any of the following medications and vaccines may not be enrolled:

• Corticosteroids, alkylating drugs, antimetabolites, radiation, immune-modulating biologics, or other immunosuppressive therapies within 90 days before Day 1 (see list in Appendix 3)

05 October 2017 Confidential Page 30 of 66

• Immunomodulating medications, including intranasal steroids, within 30 days before Day 1

- Statin medication within 30 days before Day 1 (including atorvastatin [Lipitor], fluvastatin [Lescol, Lescol XL], lovastatin [Mevacor, Altoprev], pravastatin [Pravachol], rosuvastatin [Crestor], simvastatin [Zocor], pitavastatin [Livalo])
- Intranasal medications, including over-the-counter medications within 30 days before Day 1
- IP within 30 days before Day 1
- Any vaccine within 30 days before Day 1
- Intranasal vaccine within 90 days before Day 1
- Influenza vaccine within 6 months before Day 1

#### 6.8.2 Prohibited Concomitant Medications and Vaccines

The following medications and vaccines are prohibited during the study:

- Statin medication from Day 1 to Day 29 (see list in Section 6.8.1)
- Corticosteroids, alkylating drugs, antimetabolites, radiation, immune-modulating biologics, or other immunosuppressive therapies at any time during the study (see list in Appendix 3)
- Any vaccine from Day 1 to Day 29
- Any influenza vaccine other than NasoVAX within 90 days after NasoVAX/placebo dose (receipt of influenza vaccine other than NasoVAX is discouraged through the end of the study)

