#### 2.2 Current Vaccines for Seasonal Influenza

The CDC recommends that everyone in the United States over 6 months of age receive an annual influenza vaccination. Most currently licensed vaccines are based on circulating influenza strains adapted to grow in chicken eggs. The viruses are harvested, inactivated, and combined into trivalent (containing A H1N1, A H3N2, and B strains) or quadrivalent formulations (which also contain a second B strain) and administered by injection. Other injectable vaccines currently available include a tissue culture-derived vaccine (Afluria, Seqirus), a recombinant HA protein vaccine (Flublok, Protein Sciences), and an adjuvanted inactivated vaccine (Fluad, Seqirus). In general, these vaccines are well tolerated but provide limited protection to influenza viruses that are not well matched to the vaccine strains.

05 October 2017 Confidential Page 15 of 66

An intranasal live attenuated influenza vaccine (LAIV) has been licensed since 2003 (FluMist, MedImmune). This product is replication-competent, and its use is limited to older children and adults up to age 49 years because of safety concerns. LAIV does not elicit antibody responses at the levels of other licensed influenza vaccines, but initial studies showed significant cellular immune responses, and protective efficacy was demonstrated in Phase 3 studies. More recently postmarketing studies have shown declining effectiveness, and FluMist was not recommended for use in the 2016-2017 influenza season [Seasonal 2016]. Possible reasons for the decreased effectiveness seen may be instability in viral sequence or poor immunogenicity in the presence of pre-existing antibody.

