# **3 STUDY OBJECTIVES AND ENDPOINTS**

OBJECTIVES	ENDPOINTS			
Primary Objective				
• To describe the safety profile of NasoVAX in healthy adults when administered by intranasal spray at a single dose of 1×10  , 1×10  , or 1×10  vp	
 
Reactogenicity: counts and percentages of subject with local events (nasal irritation, sneezing, nasal congestion, cough, sore throat, change in smell, change in taste, change in vision, eye pain) and systemic events (headache, fatigue, muscle ache, nausea, vomiting, diarrhea, chills, fever) for 14 days after vaccination
 
AEs: counts and percentages of subjects with AE from Day 1 to Day 29; MAEs, SAEs, NCIs from Day 1 to Day 181
 
			
Secondary Objective				
• To evaluate the humoral immune response to NasoVAX when administered by intranasal spray at a single dose of 1×10  , 1×10  , or 1×10  vp	
 
Antibody level measured by HAI in serum:         
 
GMT: the antilog of the mean of the log-transformed titers
 
GMR: the ratio of postvaccination and prevaccination GMTs within the same dose group
 
SPR: the percentage of subjects with a HAI titer ≥ 1:40
 
SCR: the percentage of subjects with either a baseline HAI titer < 1:10 and a postvaccination titer ≥ 1:40 (which is 4 times the assay lower limit of quantitation), or a baseline HAI titer ≥ 1:10 and a 4-fold increase in postvaccination HAI titer relative to baseline
 
 
 
Antibody level measured by microneutralization in serum:         
 
GMT
 
Responder rate: the proportion of subjects with 2-fold and 4-fold rise since baseline
 
 
 
			

OBJECTIVES	ENDPOINTS			
Exploratory Objectives				
• To evaluate the cellular immune response to NasoVAX when administered by intranasal spray at a single dose of 1×10  , 1×10  , or 1×10  vp	
 
SFUs to HA peptides measured by enzyme-linke ELISpot in PBMCs:
 
Geometric mean SFUs
 
Responder rate
 
			
• To evaluate the mucosal immune response NasoVAX when administered by intranasal spray at a single dose of 1×10  , 1×10  , or 1×10  vp	
 
IgA antibody level measured by ELISA:
 
GMT
 
GMR
 
			

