# 7.10.2 Serum Samples (Immunogenicity)

Serum samples will be collected and processed at the time points specified in the Schedule of Events. Collection, processing, labelling, storage and shipping instructions for these samples are provided in the laboratory manual.

Influenza virus HAI assay against A/California/04/2009(H1N1) will be performed on all samples collected.

Ad5 microneutralization, influenza microneutralization against all strains, and HAI against nonrepresented strains will be performed on samples collected on Days 1 and 29 only. A larger serum sample will be collected on Days 1 and 29 for these assays.

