#### 12.1 Analysis Populations

The following analysis populations will be used:

- Safety Population: All subjects who provide informed consent, are randomized, and receive at least 1 dose of IP. The Safety Population will be used for all safety analyses and will be analyzed according to the treatment received.
- ITT Population: All subjects in the Safety Population who have HAI assay results on Day 1 and any postvaccination time point. The ITT Population is the secondary population for immunogenicity analyses and will be analyzed according to treatment as randomized.
- PP Population: All subjects in the Safety Population that received the assigned dose of the test article in accordance with the protocol; have HAI assay results on Days 1, 15, and 29; and had no major protocol deviations affecting the primary immunogenicity outcomes as determined by the Sponsor prior to database lock. The PP Population is the primary population for immunogenicity analyses and will be analyzed as randomized.

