## 12.8.1 Secondary Endpoints (Humoral Immune Response)

The primary variable of interest for assessment of humoral immune response to the NasoVAX antigen is homologous HAI antibody titer. The following HAI immunogenicity measures and their 95% CIs will be summarized by dose group:

- GMT at baseline and postvaccination on Days 4, 8, 15, 29, 91, and 181
- GMR on Days 4, 8, 15, 29, 91, and 181 (analysis of GMR will be performed using analysis of covariance [ANCOVA] with baseline titer as a covariate)
- SPR on Days 4, 8, 15, 29, 91, and 181
- SCR on Days 4, 8, 15, 29, 91, and 181

05 October 2017 Confidential Page 47 of 66

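### Day 181 HAI summaries keep titers drawn after a non-study influenza vaccine that is discouraged but not prohibited from Day 92, so they can include a response not due to NasoVAX

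*Protocol*

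**What the plan says.** - **Vaccine rule (Protocol 6.8.2).** Any vaccine is barred from Day 1 to Day 29, and other influenza vaccine for 90 days after the dose. Beyond that, "receipt of influenza vaccine other than NasoVAX is discouraged through the end of the study".
- **Recording (6.8, 8.3.1, 8.3.2).** Vaccines are recorded to the end of the study.
- **Assay (7.10.2).** "Influenza virus HAI assay against A/California/04/2009(H1N1) will be performed on all samples collected", which includes the Day 181 serum.
- **Populations (12.1).** ITT is "All subjects in the Safety Population who have HAI assay results on Day 1 and any postvaccination time point". PP subjects must have received the assigned dose, "have HAI assay results on Days 1, 15, and 29; and had no major protocol deviations" affecting the primary immunogenicity outcomes.
- **Summaries (12.8.1).** HAI GMT, GMR and SPR are summarized by dose group through Day 181, as is "SCR on Days 4, 8, 15, 29, 91, and 181". Section 12.8 adds that missing data are not imputed.
- **Objective and measure (3).** The secondary objective is "To evaluate the humoral immune response to NasoVAX when administered by intranasal spray". The GMR is "the ratio of postvaccination and prevaccination GMTs within the same dose group".

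**The concern.** The vaccine rule and the analysis rules do not meet. A subject who takes a licensed influenza vaccine from Day 92 has broken no prohibition, so on the face of the text there is no deviation for the PP definition to act on. Both populations keep that subject, and nothing in Section 12 separates the Day 181 titer from the earlier ones. Section 2.2 describes the trivalent and quadrivalent licensed vaccines as containing an A H1N1 component, and the HAI assay is run against an H1N1 strain. It also notes that annual vaccination is recommended for nearly everyone, so receipt is plausible.

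Day 181 is the last HAI time point, the one from which persistence of the response would be read. A rise caused by another vaccine would be counted there as part of the response to NasoVAX.

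**Working it through.** The protocol gives no figure for this point: neither the uptake of other influenza vaccine nor the titer rise it would cause. The dates below come from the protocol; uptake and fold rise are assumptions shown over a range.

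**1. Dates (6.8.2; visit windows in 1.2).** Dose on Day 1, so 90 days after the dose is Day 1 + 90 = Day 91. The first day not prohibited is Day 92.
- Day 181 draw (±10 days, so Days 171 to 191): longest interval since such a vaccine is 171 − 92 = 79, 181 − 92 = 89 or 191 − 92 = 99 days.
- Day 91 draw (Days 81 to 101): at most 101 − 92 = 9 days, and only for draws late in the window.
- Day 29 and earlier: none.

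**2. Who is kept (12.1).** Take a subject dosed correctly, with HAI results on Days 1, 15, 29 and 181, who takes a licensed influenza vaccine on Day 120. ITT needs Day 1 and any later result: met. PP needs Days 1, 15 and 29 and no major deviation: met, since the vaccine was not prohibited. The Day 181 titer is counted in both.

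**3. Effect on the GMR.** Each NasoVAX dose group has n = 15 (Table 1). If k subjects have Day 181 titers raised f-fold, the group's mean log titer rises by (k/n)·log f, so the GMT and the unadjusted GMR are multiplied by f^(k/n):

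| k of 15 | f = 1 (no cross-reaction) | f = 2 | f = 4 | f = 8 |
|---|---|---|---|---|
| 1 | 1.00 | 1.05 | 1.10 | 1.15 |
| 2 | 1.00 | 1.10 | 1.20 | 1.32 |

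For example, 4^(1/15) = 1.097 and 8^(2/15) = 1.320. The ANCOVA in 12.8.1 adjusts for baseline titer, so it does not remove a rise that occurs after baseline.

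**4. Effect on SPR and SCR.** Each affected subject adds 1/15 = 6.7 points if the rise carries the subject over the criterion, and 0 if it does not or the criterion was already met. So the shift is 0 to 6.7 points for k = 1 and 0 to 13.3 points for k = 2.

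**5. Chance of at least one such subject in a group of 15.** 1 − (1 − u)^15 for an assumed uptake u of 5%, 10% or 20% is 0.54, 0.79 or 0.96.

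**6. Contrast with placebo.** With equal uptake and equal fold rise in a NasoVAX group and the 15 placebo subjects taken together, the ratio of their GMRs changes by f^(1/15 − 1/15) = 1.00. Each within-group GMR is still inflated as in step 3.

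**7. Precision lost by exclusion.** At the same SD, the log-scale 95% CI half-width changes by [t(0.975, n−k−1)/√(n−k)] ÷ [t(0.975, n−1)/√n]. For n = 15 this is 1.043 (k = 1) and 1.091 (k = 2).

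**The case against.** The strongest objection is that handling single titers after an intercurrent vaccine is ordinary SAP content. Section 12 calls itself brief and announces a detailed SAP, which is not shown. That stands as a limit: nothing here shows that the final analysis lacks a rule. It does not remove the point, because the protocol itself fixes the populations, the Day 181 time point and the vaccine rule, and together they count the titer.

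Second, the protocol does address the risk: it bans the vaccine for 90 days, discourages it afterwards and records every vaccine. This is fair. It makes affected samples identifiable, but it does not say what to do with them.

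Third, the trial has a concurrent randomized placebo group, and individual assignments stay blinded for study personnel until final lock (12.10). A common rise would show there, and step 6 gives no change in the contrast under equal uptake and effect. This stands for between-group comparison; it does not correct the GMR, SPR or SCR, which are within-group measures. Nor would exclusion remove rises from natural influenza exposure, for which placebo remains the reference.

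Fourth, excluding samples on post-randomization behaviour, with no imputation, may itself select subjects. This also stands, and it is why an all-samples summary is needed alongside.

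A reader might infer that the Day 181 results will be biased upward. The documents do not support that: they do not establish that any subject is vaccinated or that the vaccine's H1N1 component raises titers to A/California/04/2009, and Section 2.2 says HA forms vary from year to year. A reader might also compute larger effects by showing placebo by cohort, five subjects at a time; Section 12.2 speaks only of the NasoVAX and placebo groups and states no such display.

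**Conclusion.** The point holds as a gap between the protocol's stated rules. From Day 92 another influenza vaccine is discouraged but not prohibited, and the stated populations and summaries keep a Day 181 titer drawn after it. The within-group Day 181 HAI results can then include a response not due to NasoVAX.

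How much is unknown. The factors of 1.05 to 1.15 and the shift of up to 6.7 points for one affected subject of 15 rest on an assumed 2- to 8-fold rise. The effect is nil if nobody is vaccinated or there is no cross-reaction.

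The reach is one late time point of a secondary, descriptive endpoint in a study not sized for power (12.9). The reactogenicity and adverse event analyses, HAI results through Day 29 and the interim analysis are untouched, and Day 91 is exposed only marginally. Priority is minor.

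**What to change.** Unless the SAP already does this, state in Section 12.8.1, before any by-arm data are released (Section 6.4 withholds these until after the interim analysis):

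- HAI results from samples drawn after a recorded non-study influenza vaccine are excluded, sample by sample, from the main Day 181 summaries and from any affected Day 91 summary. The subject's earlier visits are kept, and excluded titers are treated as missing under the existing no-imputation rule.
- An all-samples summary is given as a sensitivity analysis, with the number of affected subjects by group and their vaccination and draw dates.

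Exclusion is proposed as the main summary because the stated objective is the response to NasoVAX. No change to the vaccine-use rule is proposed.

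The change is to analysis wording only, since the vaccine data are already collected. It costs a CI half-width about 4% or 9% wider if 1 or 2 of 15 titers are removed. It also carries possible selection from excluding on post-randomization behaviour, which the all-samples summary puts in view.
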